10.7 Handling of Dropouts or Missing Data

Participants who discontinue study drug or withdraw consent will be included in mITT analyses if they received at least one dose of study drug. In the absence of a substantial difference in the

rate of withdrawal, the planned repeated measures analysis should prevent bias in estimating treatment differences. If rates of withdrawal are notably higher among participants randomized to SYN120, a nonparametric analysis that assigns the worst observed outcome to participants who withdraw prior to Week 16 will be used a conservative estimate of treatment benefit. Additional sensitivity analyses may be pursued to impute missing values or otherwise construct models for unobserved outcomes.

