## 1. INTRODUCTION

This Statistical Analysis Plan (SAP) defines the analysis samples, specifies the analysis, and guides the interpretation of results from the [SYN120-CL03](#) or SYNAPSE clinical trial. The SAP supplements the clinical protocol. Readers are encouraged to refer to the clinical protocol for details on the rationale for the intervention, eligibility criteria, conduct of the trial, clinical assessments and the timing of their use in the trial, definitions and reporting of adverse events, data management conventions, and regulatory oversight and compliance procedures. The reader is referred to the Investigator's Brochure for additional details on physiochemistry and pre-clinical and clinical pharmacokinetics and safety of the investigational product, SYN120.

In case of discrepancies between the SAP and the clinical protocol concerning matters of analysis, the SAP is authoritative. On all other matters, the clinical protocol is authoritative.

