## 3.3. Measurement Definitions

### 3.3.1. CDR Measures

The CDR ([Wesnes et al. 1992](#)) is a computerized neuropsychological test battery to assess cognitive tasks based on measures of choice reaction time, vigilance, and the sensitivity and speed of digit, word and picture recognition. The stimuli are presented on a computer screen and the subjects respond by pressing either a “Yes” or “No” on a response box. Detailed of the assessments are described in the clinical protocol.

Continuity of Attention (COA) measures the ability to sustain attention and avoid error. COA is calculated as  $(VIGACC*0.45) + (CRTACC*0.5) - VIGFA$ , where VIGACC is digit vigilance accuracy, CRTACC is choice reaction time accuracy, and VIGFA is digit vigilance false alarms. Higher COA scores represent greater sustained attention and avoidance of errors.

Quality of Episodic Memory (QEM) measures the ability to store, hold, and retrieve information of an episodic nature. QEM is calculated as  $(DRECOACC + DRECNACC - 100) + (DPICOACC + DPICNACC - 100) + ((IRCL - IRCLERR)*100 / 12) + ((DRCL - DRCLERR)*100 / 12)$ , where DRECOACC is word recognition original stimuli accuracy, DRECNACC is word recognition new stimuli accuracy, DPICOACC is picture recognition original stimuli accuracy, DPICNACC is picture recognition new stimuli accuracy, IRCL is immediate word recall words recalled, IRCLERR is immediate word recall errors, DRCL is delayed word recall words recalled, and DRCLERR is delayed word recall errors. Higher QEM scores represent greater ability to store, hold, and retrieve information of an episodic nature.

Quality of Working Memory (QWM) measures the ability to store and retrieve information in working memory. QWM is calculated as SPMSI + NWMSI, where SPMSI is the sensitivity index for spatial working memory and NWMSI is the sensitivity index for numeric working memory. Sensitivity index ([Frey and Collier 1973](#)) measures the ability to identify previously presented stimuli and reject stimuli which were not previously presented. A score of 1 represents perfect discrimination; all of the previously presented stimuli are correctly identified and all distractor stimuli are correctly rejected as being novel. A score of -1 represents perfect reverse discrimination; none of the previously presented stimuli are correctly identified, and all distractor stimuli are selected as being novel. A score of 0 represents chance performance with no

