### 3.8.2. Secondary Analyses of the Primary Efficacy Endpoint

Several secondary analyses will be investigated to assess sensitivity of our estimates of treatment effect to alternative modeling assumptions and alternative handling of the CDR data.

- Random-slopes model: The repeated-measures covariance will be replaced with random participant-level intercepts and slopes with unstructured covariance. Data from Early Termination visits will be placed at their observed follow-up time. The following SAS code

specifies the model and the linear contrasts used to estimate treatment-specific and treatment-dependent changes over 16 weeks:

```
proc mixed data=xxx method=reml;
  class site id trtrnd;
  model Value = week trtrnd*week;
  random intercept / subject=site type=vc;
  random intercept week / subject=id(site) type=un;
  estimate "1|Active |Chg 16" intercept 0 week 16 trtrnd*week 16 0 / cl;
  estimate "1|Placebo|Chg 16" intercept 0 week 16 trtrnd*week 0 16 / cl;
  estimate "2|ActvPbl|Chg 16" intercept 0 week 0 trtrnd*week 16 -16 / cl;
```

- Shared-baseline, repeated-measures ANOVA model with pMI for missing data: The shared-baseline repeated-measures ANOVA model described above for the primary analysis will be applied to datasets generated by placebo multiple imputation (Ayele et al. 2014). Fifty imputed datasets will be generated for a given endpoint.
- Cochran-Mantel-Haenszel row mean score LOCF: 16-week change scores will be compared by mean score test using modified ridit scores stratified by clinical site. The last observed CDR COA value will be carried forward when CDR COA values are not available from the Week 16 visit. The following SAS code specifies the model:

```
proc freq data=xxx;
  table site * trtrnd* Value / cmh scores=modridit;
```

- Cochran-Mantel-Haenszel row mean score WO: 16-week change scores will be compared by mean score test using modified ridit scores stratified by clinical site. The worst observed CDR COA 16-week change from baseline will be imputed when CDR COA values are not available from the Week 16 visit.
- PP sample: The primary efficacy model and the secondary random-slopes model will be applied to the PP sample.
- Alternative CDR data: The primary efficacy model and the secondary random-slopes model will be applied to mITT and PP samples using the raw CDR data.

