### **3.8.6. Missing Data**

Baseline values for efficacy endpoints will be determined from the last non-missing data collected prior to the first dose of study medication. The planned repeated-measures model yields estimates that are unbiased conditional on the observed scores under a missing at random assumption. In addition, a secondary analysis of the primary endpoint will use placebo-based multiple imputation of missing data. The Cochran-Mantel-Haenszel row mean score LOCF and WO analyses provide estimates of treatment effect when normality assumptions are violated. Additional sensitivity analyses may be pursued to impute missing values or otherwise construct models for unobserved outcomes if more than 20% of participants are missing follow-up data for any reason.

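### The SAP drops the protocol's trigger for worst-outcome scoring, so this secondary analysis tilts towards SYN120 whenever placebo has more missing Week 16 scores

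*SAP*

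**What the plan says.** Protocol 10.7 sets a directional condition: "If rates of withdrawal are notably higher among participants randomized to SYN120, a nonparametric analysis that assigns the worst observed outcome to participants who withdraw" before Week 16. It gives the purpose as well: the analysis "will be used a conservative estimate of treatment benefit".

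SAP 3.8.2 lists a WO analysis among the secondary analyses of the primary endpoint. The test is described as follows: "16-week change scores will be compared by mean score test using modified ridit scores stratified by clinical site". The imputation rule is: "The worst observed CDR COA 16-week change from baseline will be imputed when CDR COA values are not available from the Week 16 visit". It has no trigger and no reference to which arm has more missing data, and it is not limited to withdrawals.

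SAP 3.8.6 does not restore the condition. It gives a different purpose: "The Cochran-Mantel-Haenszel row mean score LOCF and WO analyses provide estimates of treatment effect when normality assumptions are violated".

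SAP section 1 settles precedence: "In case of discrepancies between the SAP and the clinical protocol concerning matters of analysis, the SAP is authoritative". The unconditional rule therefore applies. SAP 3.8.3 carries the same models over to the key secondary endpoint, Quality of Episodic Memory.

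**The concern.** Worst-outcome scoring is conservative for a drug only when the drug arm carries at least as many of the worst scores as the control arm. The protocol's trigger secured that. Without it, the direction of the penalty depends on which arm happens to have more missing Week 16 values. If that is placebo, whether through withdrawal, a missed visit or a failed computer session, the extra worst ranks fall on placebo and the comparison shifts towards SYN120 with no difference in any observed score.

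What is at stake is interpretation. These analyses are there to show whether the treatment estimate is sensitive to assumptions. A significant WO result is easily read as a stringent check that was passed, because the protocol describes it that way. For the key secondary endpoint this matters a little more, since SAP 3.8.5 allows that endpoint alone to be accepted as evidence of benefit.

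**Working it through.** **Inputs.** 80 randomised, 40 per arm, 15% loss, effect size 0.69, two-sided alpha 0.05 (Protocol 10.8). Blocks of 4, stratified by site (SAP 2.5). 20 sites (SAP 2.3); 12 in Protocol 3.1.2, run as an alternative. Direction of COA (SAP 3.3.1): "Higher COA scores represent greater sustained attention and avoidance of errors", so the worst change is the most negative one. The split of missing scores between arms is not in the documents and is assumed throughout.

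**The plan's own figure.** Evaluable per arm: 40 × 0.85 = 34. Power ≈ Φ(0.69 × √(34/2) − 1.96) = Φ(2.845 − 1.96) = Φ(0.885) = 81.2%. The exact noncentral t gives 80.05%. The stated 80% reproduces.

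**Mechanism in one site of four.** The modified ridit score is rank/(n + 1), giving 0.2, 0.4, 0.6 and 0.8. Suppose one placebo score is missing, takes the lowest rank, and is not tied. With no treatment effect, each of the other three patients has expected score (0.4 + 0.6 + 0.8)/3 = 0.6. The SYN120 mean is then 0.6 and the placebo mean (0.2 + 0.6)/2 = 0.4. The expected difference is 0.2 in SYN120's favour, where it would be 0 with nothing missing.

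**Simulation, no treatment effect.** Change scores are normal with SD 1. Missing scores are chosen completely at random and set to the worst observed change pooled over both arms. The test is the site-stratified mean score test. Nominal rate in SYN120's favour: 5%/2 = 2.5%.

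Fixed missing counts out of 40 (2,500 runs per cell):

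| Missing SYN120 v placebo | Favours SYN120, 20 sites | 12 sites |
|---|---|---|
| 0 v 0 | 2.1% | 2.1% |
| 6 v 6 | 0.8% | 0.6% |
| 4 v 8 | 6.6% | 7.4% |
| 2 v 6 | 7.8% | 8.0% |
| 0 v 6 | 14.6% | 15.4% |
| 2 v 10 | 22.6% | 26.2% |
| 6 v 2, 8 v 4, 10 v 2 | 0.0% to 0.1% | 0.0% to 0.1% |

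In the four rows with more missing on placebo, the mean difference moves towards SYN120 by 0.24 to 0.48 SD. That is 0.24/0.69 = 35% to 0.48/0.69 = 70% of the design effect.

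Missing counts left random, 20 sites, all 80 analysed:
- At 15% in both arms, two-sided rejection is 4.8% to 4.9%.
- At 20% placebo v 10% SYN120, about 9% to 10% of runs favour SYN120.
- At 20% v 5%, about 17% to 18% do.
- At 25% v 5%, about 28% to 29% do.

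These exceed the fixed-count results because chance can widen the gap in counts.

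**Allowing for the mITT definition.** SAP 3.5 requires a valid post-treatment COA, so a patient lost before any such score is excluded, not imputed. If half the missing patients are excluded (an assumption), two-sided rejection at 20/10, 20/5 and 25/5 is about 6.7%, 7.5% and 12.2%, nearly all in SYN120's favour. If three quarters are excluded, it is about 6% in all three.

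**The case against.** The strongest case for the SAP is this. WO is one of several secondary analyses, beside random slopes, placebo multiple imputation, LOCF, per-protocol and raw-data runs. SAP 3.8.1 ties evidence of benefit on COA to one contrast in the primary model. The SAP does not call WO conservative. Running it in every case avoids a judgement on the protocol's trigger, which has no numerical definition. Where the trigger would have fired, the SAP still runs WO, and it is then conservative. SAP 3.10.1 reports withdrawals and reasons by arm. And if placebo patients leave for lack of benefit, ranking them worst is a defensible composite outcome and not plainly a bias.

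Most of that stands and limits the point. It does not remove it. Withdrawals by arm are not the same as unavailable Week 16 scores, which is what the SAP rule acts on. The composite argument fails for scores missing for reasons unrelated to outcome, and the rule covers those too. SAP 3.8.6 places WO under missing data without saying when its direction reverses.

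Three stronger readings are tempting and are not supported:
- That the SAP turned a one-arm rule into a two-arm rule. Once triggered, Protocol 10.7 already scores withdrawals as worst without naming an arm. What changed is the trigger and the widening to any unavailable value.
- That a WO result could carry a claim of benefit by itself. No text lets it replace the primary contrast or the rule in SAP 3.8.5.
- That the protocol's direction means worst scores for SYN120 only, with a central value for placebo. Neither document contains such a rule, and it would penalise SYN120 even with equal missingness.

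**Conclusion.** The point holds as a conditional defect in one secondary analysis, repeated for the key secondary endpoint. If placebo has more missing Week 16 scores, WO as written is anti-conservative. The chance of a significant result favouring SYN120 with no effect is about 10% at 20% v 10% missing and up to 29% at 25% v 5%, or about 6% to 12% if half the missing patients are outside mITT, against 2.5%.

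The sizes rest on assumed missingness splits, scores missing at random, and a worst value pooled over both arms, since the SAP does not say pooled or by arm. The SAP also does not say whether an Early Termination score that SAP 3.8.1 assigns to Week 16 counts as available for WO. That affects how many scores are imputed, not the direction for a given excess on placebo. With equal missingness WO favours neither arm. The primary model, placebo multiple imputation and LOCF do not use the rule.

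**What to change.** In SAP 3.8.2 and 3.8.6, restore the protocol's direction. State that WO is used and interpreted as a conservative check only when SYN120 has at least as many missing Week 16 scores as placebo. Otherwise it is reported, if at all, beside the missing counts by arm and is not cited as support for benefit. Apply the same wording to Quality of Episodic Memory. Because the condition depends on a count, say in the same place whether an Early Termination score assigned to Week 16 counts as available.

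Under this condition the simulated rate in SYN120's favour was 0.0% to 0.8% in every fixed-count case with missing scores that was examined, so the check does what the protocol intended.

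The cost is a sentence or two before unblinding, with no new data or programming of substance. The downside is that WO cannot be cited in SYN120's favour when placebo loses more patients. WO is also a severe test where it does apply: with a true effect of 0.69 and 20 sites, its power was 49% at 6 v 6 missing and 17% at 8 v 4 (SYN120 v placebo). A non-significant WO result there should not be read as evidence against benefit.

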### 3.8.3. Secondary Efficacy Endpoints

The key secondary efficacy endpoint will all be analyzed using the same analysis samples and models as specified for the primary efficacy endpoint in [Sections 3.8.1](#) and [3.8.2](#). Non-key secondary efficacy endpoints and exploratory efficacy endpoints will all be analyzed using the mITT sample and the primary efficacy analysis described in [Section 3.8.1](#). Variables that are strictly positive and strongly right-skewed (e.g., CDR POA, CDR SWM, and other CDR measures of reaction time) will be analyzed on their original scale and after log-transformation. Estimates from analysis of log-transformed data will be back-transformed for reporting.

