10.1 Definition of Analysis Sets

Safety Sample (SS): The SS will consist of all randomized patients who received at least one dose of IMP.

Modified Intention-to-Treat (mITT) Sample: The mITT sample will consist of all randomized patients who received at least one dose of IMP and who have at least one valid baseline and at least one valid post-baseline assessment of the primary efficacy endpoint.

Per-Protocol Set (PP): The PP will consist of a subset of the mITT sample, excluding any participants or observations potentially affected by important protocol deviations that may influence the validity of the data for testing efficacy and as specified in the SAP prior to breaking the blind.

All safety variables will be summarized using the SS. All efficacy variables will be summarized using the mITT sample. The PP will be utilized for sensitivity analyses to estimate efficacy among participants tolerant of study drug and with less reliance on model assumptions required to extrapolate after any loss to follow up.

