### **3.5. Analysis Samples**

The following analysis samples will be used for testing safety, tolerability, efficacy, and pharmacokinetic endpoints:

- Safety and Tolerability (ST) Sample: Participants who are eligible, randomized, and take at least one dose of study drug, classified according to the actual treatment received.
- Efficacy Modified Intent-to-treat (mITT) Sample: Participants who are eligible, randomized, have at least one valid pre-treatment and at least one valid post-treatment CDR COA measurement, and take at least one dose of study drug, classified according to their randomized treatment assignment. This sample will include observations made after discontinuation of study drug should any such participants remain on study.
- Efficacy Per-protocol (PP) Sample: Participants who are eligible, randomized, have at least one valid pre-treatment and one valid post-treatment CDR COA measurement, take at least one dose of study drug, and meet all other major protocol compliance criteria specified prior to unblinding, classified according to the actual treatment received. Observations made after permanent discontinuation of study drug (whether due to intolerance, early termination, loss to follow-up, or death) will be omitted, but completion of follow-up on study drug will not be required. Any other individual observations affected by important protocol deviations may also be excluded, as specified prior to unblinding.
- Pharmacokinetic (PK) Sample: Participants in the ST sample who have at least one valid determination of their plasma SYN120 concentration.

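### A treated patient with no valid baseline or no valid post-baseline Continuity of Attention score is dropped from every secondary and exploratory efficacy analysis, even where those other measures were completed

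*SAP*

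**What the plan says.** SAP 3.5 (Analysis Samples) admits to the mITT sample eligible, randomised participants who "have at least one valid pre-treatment and at least one valid post-treatment CDR COA measurement, and take at least one dose of study drug". The per-protocol sample carries the same condition: its members must "have at least one valid pre-treatment and one valid post-treatment CDR COA measurement, take at least one dose of study drug".

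SAP 3.8.3 (Secondary Efficacy Endpoints) then applies these samples to everything else. For QEM: "The key secondary efficacy endpoint will all be analyzed using the same analysis samples and models as specified for the primary efficacy endpoint". For the rest: "Non-key secondary efficacy endpoints and exploratory efficacy endpoints will all be analyzed using the mITT sample".

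Protocol 10.1 agrees. Its mITT sample is limited to dosed patients "who have at least one valid baseline and at least one valid post-baseline assessment of the primary efficacy endpoint", and it adds: "All efficacy variables will be summarized using the mITT sample".

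Protocol 10.7 reads more loosely: "Participants who discontinue study drug or withdraw consent will be included in mITT analyses if they received at least one dose of study drug". The SAP Introduction makes the SAP authoritative on matters of analysis, so SAP 3.5 governs.

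Neither document defines an endpoint-specific efficacy set. Neither plans an analysis of the secondary efficacy scales in all treated patients.

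**The concern.** COA is built from digit vigilance accuracy, choice reaction accuracy and vigilance false alarms (SAP 3.3.1). None of the other scales uses these. PDAQ-15 and NPI are reported by the caregiver. QEM comes from the recall and recognition tasks and shares no component with COA. A missing COA is therefore no reason to discard a valid value on those measures.

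Whether a patient has a valid post-baseline COA is known only after randomisation and may be related to cognitive state. The PDD criteria in Protocol 14.2 list impaired, fluctuating attention among the features of the disease. SAP 3.8.6 defends the repeated-measures model as unbiased given the observed scores under missing at random. Deleting observed scores because a different test is missing weakens that defence.

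Two features raise the stakes. SAP 3.8.5 allows significance on QEM alone to be accepted as evidence of benefit. In addition, SAP 3.5 does not define a valid COA. SAP 3.3.2 provides a raw and an expert-adjudicated CDR dataset, and the SAP does not say which one decides membership. Adjudication of a CDR record could thus settle whether a caregiver's NPI counts.

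**Working it through.** **1. Who is lost.** The CDR is given at Baseline, Week 8, Week 16 and Early Termination (ET). The two screening sessions are training and are not evaluated (Protocol 7.1). After baseline, the non-CDR efficacy scales are collected only at Week 16 or ET (SAP 2.7). SAP 3.8.1 assigns ET data to the next scheduled visit, so an ET score can supply the post-treatment COA. Applying SAP 3.5 to a treated patient with complete Week 16 or ET data on the other scales:

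| Valid baseline COA | Valid COA at Week 8 | Valid COA at Week 16 or ET | In mITT | Other scales used |
|---|---|---|---|---|
| yes | yes | no | yes | yes |
| yes | no | yes | yes | yes |
| yes | no | no | no | **no** |
| no | any | any | no | **no** |

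Only the last two rows lose data.

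**2. The plan's own figure.** Inputs from SAP 3.4 and Protocol 10.8: 80 randomised 1:1, 15% loss, effect size d = 0.69, two-sided alpha 0.05, two-sample t-test. Evaluable per arm: 40 × 0.85 = 34. Noncentrality is d × √(n/2) = 0.69 × √17 = 2.84, with 66 degrees of freedom. Power is 80.05%, so the stated figure of at least 80% reproduces. It belongs to COA and serves below only as a yardstick.

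**3. Lost precision.** Assume k patients per arm have valid data on a secondary scale but are excluded for lack of COA, and that 34 per arm would otherwise be available. Variance rises by the factor 34/(34 − k).

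| k per arm | n per arm | Variance factor | Power at d = 0.69 |
|---|---|---|---|
| 0 | 34 | 1.00 | 80.0% |
| 1 | 33 | 1.03 | 78.8% |
| 2 | 32 | 1.06 | 77.5% |
| 3 | 31 | 1.10 | 76.2% |
| 4 | 30 | 1.13 | 74.8% |

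At k = 2 the standard error rises by √(68/64) − 1 = 3.1%.

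**4. Selection.** Assume the worst fraction f on COA is removed from one arm only, and that COA correlates r with the other scale (bivariate normal). The retained mean moves favourably by r × φ(z)/(1 − f), where z is the normal quantile with lower tail f. For f = 5%: φ(1.645)/0.95 = 0.109, so 0.3 × 0.109 = 0.03 and 0.7 × 0.109 = 0.08 SD.

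| f | r = 0.3 | r = 0.5 | r = 0.7 |
|---|---|---|---|
| 5% | 0.03 | 0.05 | 0.08 |
| 10% | 0.06 | 0.10 | 0.14 |
| 15% | 0.08 | 0.14 | 0.19 |

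Five percent of 34 is 1.7 patients. If both arms lose similarly, the shifts largely cancel in the treatment difference and only the loss of precision remains.

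**The case against.** The strongest case is that the condition will rarely bite. Patients have two CDR training sessions (Protocol 7.1) and a screening MoCA of at least 10 (Protocol 4.1). Unpredictable motor fluctuations that would interfere with cognitive testing are excluded (Protocol 4.2). The CDR comes first among the assessment instruments at Baseline, Week 16 and ET, to limit fatigue. To lose Week 16 data after a valid baseline COA, a patient must complete the other scales and yet never produce a valid post-baseline COA. For the other CDR measures, a patient who cannot do the battery usually has little to lose. This stands, and it limits the likely size.

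It can also be said that one common efficacy set, prespecified in both documents, is a recognised choice that keeps N constant across tables. Non-key results in this Phase 2a trial carry only nominal p-values (SAP 3.8.5). That lowers the stakes but gives no reason to discard observed data, and it does not cover QEM. The SAP already fits the same model to UPDRS in the Safety and Tolerability sample (SAP 3.9.6), with no COA condition.

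A reader might infer that failing or refusing the Week 16 CDR is enough to remove a patient's Week 16 NPI and PDAQ-15. It is not: a valid baseline and Week 8 COA keep the patient in. Nor are all scales affected, since UPDRS and the safety outcomes do not depend on COA. A reader might also expect a large gain because the shared-baseline model accepts patients with a baseline value only. Such patients add almost nothing to the Week 16 contrast, and ADCS-CGIC has no baseline value. The gain comes from patients with observed post-baseline data.

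**Conclusion.** The point holds within the limits of the first table. The condition is in the governing text, has no link to most of the outcomes it filters, and is partly determined after randomisation. It concerns the secondary and exploratory efficacy analyses and leaves UPDRS and safety untouched.

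Its size cannot be derived from the documents, because no expected count of patients lacking COA but having other data is given. It is probably small. The illustrations are a power loss from 80.0% to between 78.8% and 74.8% for 1 to 4 patients lost per arm, and a shift of about 0.03 to 0.08 SD for one-sided removal of the worst 5% on COA. They rest on assumed counts, assumed correlations of 0.3 to 0.7, and an effect size planned for COA.

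A reader might be tempted to quote 0.11 SD for the 5% case and set it against the 0.69 design effect. That would require selection on the secondary scale itself, whereas the condition selects on COA availability. The 0.69 was not planned for any secondary scale. It would equally go too far to state that the patients lost will be the most impaired, or that losses will differ by arm. Both are plausible, but the documents do not establish either.

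The change is worth making because it recovers observed data at almost no cost.

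**What to change.** In SAP 3.8.3, specify that each secondary and exploratory efficacy endpoint, including QEM, is analysed in all randomised patients who took at least one dose and have valid data on that endpoint, by assigned arm. For ADCS-CGIC this means a Week 16 or Early Termination rating. Keep the COA-based mITT as a sensitivity analysis for these endpoints. Define a valid COA and say whether the adjudicated or the raw dataset decides it. Reconcile Protocol 10.7 with SAP 3.5, so that both state the same condition for mITT membership.

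The cost is wording, to be settled before unblinding. The downside is that N will differ by endpoint in the tables. SAP 3.6 calls for a baseline summary of each analysis sample, so the text should also say whether the endpoint-specific sets need their own summaries.
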